## 7.2 Procedural Information

For information describing the procedural steps and materials necessary for appropriate use of the NIRxcell Stent System, refer to the US Instructions for Use.

Additionally, note the following:

- *Start of the Procedure and Enrollment*

The start of the procedure is defined as the time of arterial cannulation. Actual enrollment in the study occurs at the time the study device is introduced into the body. If the angiogram performed at the index procedure indicates that the subject is not a candidate for the study, this subject is not considered enrolled.

- *Angiographic Protocol Requirement*

- Following intracoronary injection of 50–200 µg nitroglycerin (NTG), obtain baseline angiograms using at least  $\geq 2$  near orthogonal views, best demonstrating the coronary artery stenosis, as specified in the angiographic protocol.
- Before stent placement, obtain a single working view of the coronary artery stenosis, as specified in the angiographic protocol.

- *Pre-Dilatation*

If the target lesion fulfills eligibility criteria, the target lesion must be pre-treated with standard percutaneous transluminal balloon angioplasty. This clinical protocol does not allow for direct stenting of the target vessel.

Attention must be paid to the pre-dilatation technique to avoid balloon injury to any segment of the vessel that will not be entirely covered by the stent ('geographical miss').

Pre-dilatation must be performed using a balloon with the following 3 characteristics:

1. A diameter  $\geq 0.5$  mm smaller than the treatment stent.
2. A length matching or shorter than the lesion length to be dilated (to avoid dilatation of the vessel wall adjacent to the stent).
3. A length shorter than the stent to be implanted.

The use of other therapy (e.g. cutting balloons, atherectomy, laser, thrombectomy, etc.) is not allowed.

- *Selection of Appropriately Sized Stent*

Select an appropriately sized stent based on angiographic vessel measurements (approximately 2–4 mm longer than the measured shoulder-to-shoulder lesion length, with a stent to distal reference vessel ratio of 1:1 or 1.1:1.0). The intention should be to cover the whole lesion with 1 stent of adequate length.

**Note:** Additional NIRxcell Stent Systems should be used, at the physician's discretion, for sub-optimal result, or in the event of bailout procedures, as defined below.

- *Bailout Procedures*

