The intention should be to cover the index lesion with 1 stent of adequate length. Bailout procedures and additional stenting for sub-optimal results should be avoided unless required for subject safety. If a subject enrolled in the study experiences a major dissection or an occlusive complication (as evidenced by decreased target vessel flow, chest pain, or ischemic ECG changes that do not respond to repeat balloon inflations, NTG, intracoronary verapamil, intracoronary diltiazem, or lytic agents), bailout procedures may be performed. For bailout procedures or in the event of a sub-optimal result, further stenting may be employed, at investigator's discretion, using the NIRxcell Stent Systems, as required.

- *End of the Procedure*

The end of the procedure is defined as the time that the final guiding catheter is withdrawn from the subject. Closure of the arterial puncture site will be performed as per laboratory

standards. The hemostasis introducer sheath(s) may be removed when the subject's activated clotting time (ACT) is <150 seconds or per the physician's discretion. If a guide catheter is introduced once the procedure is considered over, as defined above, or the subject is returned to the procedure room and interventional therapy is performed, this should be considered a repeat intervention.

- *Adverse Events Recording*

All adverse events (AEs) occurring following informed consent signature must be recorded.

**Note:** Bailout procedures performed during the same catheterization as the index stenting procedure shall be considered part of the index procedure.

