### **Detailed Explanations**

**Adverse Events:** Adverse events occurring (1) from time of index procedure to 30 days follow-up contact, (2) From 30 days follow up contact to 1 year follow-up contact, (3) From 1 year follow-up contact to 2 years follow-up contact, and (4) From 2 years follow-up contact to 3 years follow-up contact, will be recorded. In the event of an AE that is associated with repeat

angiography/revascularization, the event related coronary angiograms and catheterization report must be captured and submitted to the data center within 10 working days of knowledge of the event. Angiographic data collected during any repeat procedure on the target vessel must be made available to the CEC for an independent review and assessment. Likewise, the angiographic images should be submitted to the core laboratory for an independent review and assessment of the target lesion and study stent.

**12-Lead ECG:** According to each site's standard of care.

**CBC With Differential:** Hematology testing due to anti-platelet therapy should follow the routine standard of care.

**CK, CK-MB and Troponin:** CK, CK-MB or troponin will be obtained pre-procedure (within 24 hours of the index procedure). Post procedure, CK and CK-MB will be measured at 6- 8 hours, 12-16 hours and 20-24 hours post procedure (or upon discharge, whichever comes first). If any CK elevation (CK above ULN) is noted post procedure, CK and CK-MB measurements will continue to be performed every 8 hours for 24 hours starting from when the first elevation is noted and recorded on the appropriate eCRF. If total CK values are within normal ranges, CK-MB measurements may not be performed (per hospital standards). However, it is strongly encouraged that CK-MB measurements are obtained with every total CK drawn, even if CK values are within normal limits. It is also recommended that sites collect CK and CK-MB preferentially over troponin in the peri-procedural period subsequent to the index procedure. In the case where CK and CK-MB are not available, troponin can be used.

**Relevant Medications:** Statins, ACE-I, ARB, beta-blockers and anti-platelets.

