2 STUDY OBJECTIVES AND DESIGN

2.1 Overall Study Objectives

The purpose of this study is to collect and analyze additional information about the safety and effectiveness of the NIRxcell stents in the treatment of *de novo* stenotic lesions in native coronary arteries. Data will be collected at 30 days, 9 months and 1, 2 and 3 years post–index stenting procedure. The primary objective is to assess the incidence of TVF within 3 years after treatment with the NIRxcell Stent System.

The long-term safety of the stenting procedure, including the occurrence of complications, will be evaluated through clinical data obtained before, during and after stent placement. Initial effectiveness of stent placement will be evaluated by determining acute success, including device success, lesion success and procedure success. The primary clinical outcome of TVF at 3 years post–index stenting procedure as well as a number of secondary outcomes will be used to

determine the long-term clinical effectiveness of treating native coronary artery lesions with the investigational product.

The NIRTRAKS Post-Market Study will be performed according to the World Medical Association Declaration of Helsinki, and FDA regulation 21 Code of Federal Regulations (CFR) parts 803, 812, 50 & 54. The data collected will be used to support the post-market requirements for the NIRxcell Stent System.

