2.2.5 Scheduled Study Procedures

Table 1: Summary of Study Procedures from Screening through End of Follow-Up

Study Requirement	Screening		Procedure	Post-Procedure					
	Within 7 Days Prior to Procedure	24 Hours Prior to Procedure		Hospital Discharge	30 Days (± 2 Weeks)	9 Months (± 1 Month)	1 Year (± 1 Month)	2 Years (± 1 Month)	3 Years (± 1 Month)
Informed consent	X								
Medical history	X								
Clinical assessment and physical exam	X			X					X(7)
Telephone assessment					X	X	X	X	X
CBC w/differential (1)	X								
Serum creatinine	X								
INR, APTT	X								X(7)
Pregnancy test	X(2)								
CK/CK-MB/ troponin		X(3)		X(6)					X(7)
12-lead ECG		X(4)							X(7)
Record of relevant medications (5)		X		X	X	X	X	X	X
Coronary angiography			X						
Stenting			X						
Record of adverse events			X	X	X	X	X	X	X

APTT: activated partial thromboplastin time; CBC: complete blood count; CK: creatinine kinase; CK-MB: creatinine kinase myocardial band; ECG: electrocardiogram; INR: international normalized ratio

(1) Collection of CBC differentials during the index hospitalization should be done as per the respective institutions standard of care. However, if the white blood count (WBC) is abnormal, it is recommended to perform the CBC differential before and after the procedure.

(2) For females of childbearing potential.

(3) Pre-procedure cardiac enzymes: CK, CK-MB or troponin performed within 24 hours prior to the procedure may be used as the baseline cardiac enzymes provided there have been no signs or symptoms of myocardial ischemia between the time of cardiac enzymes test and the time of arterial access.

(4) Pre-procedure 12-lead ECG: an ECG performed within 7 days prior to the procedure may be used as the baseline ECG provided there have been no signs or symptoms of myocardial ischemia between the time of ECG and the time of arterial access.

(5) Relevant medications: statins, angiotensin converting enzyme inhibitors (ACE-I), angiotensin receptor blockers (ARB), beta-blockers and anti-platelets.

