4.4 Adverse Events

A Treatment Emergent Adverse Event (TEAE) is an event that emerges, or a pre-existing event that worsens, any time during or after stent implantation. Adverse events will be coded by the MedDRA system version 18.1 or later. The per-event and per-patient incidence of TEAEs will be presented overall and by MedDRA system organ class and preferred term. This will be repeated for serious TEAEs.

5 TABLES, FIGURES, and LISTINGS

Table 1.1a Primary Endpoints – Intention-to-Treat Analysis Set

Primary Endpoint	ITT Subjects with Available Data (N=xx subjects)	Two-sided Binomial Exact 95% CI
TVF at 3 years	xx.xx% (xx/xx)	[xx.xx%, xx.xx%]
Cardiac Death	xx.xx% (xx/xx)	[xx.xx%, xx.xx%]
Target Vessel MI	xx.xx% (xx/xx)	[xx.xx%, xx.xx%]
Clinically-driven TVR	xx.xx% (xx/xx)	[xx.xx%, xx.xx%]

Note: Events defined for the period of 3 year post-procedure follow up are reported for patients with at least 1050 days of follow-up or with event to 3 years (1080 days).

Table 1.1b Primary Endpoints – Per-Protocol Analysis Set

Table 1.2 Secondary Endpoints – Intention-to-Treat Analysis Set

	ITT Subjects (N=xx subjects)	Two-sided Binomial Exact 95% CI
TVF at 9 months	xx.xx% (xx/xx)	[xx.xx%, xx.xx%]
All Cause Death		
30-day	xx.xx% (xx/xx)	[xx.xx%, xx.xx%]
1-year	xx.xx% (xx/xx)	[xx.xx%, xx.xx%]
2-year	xx.xx% (xx/xx)	[xx.xx%, xx.xx%]
3-year	xx.xx% (xx/xx)	[xx.xx%, xx.xx%]
Cardiac Death		
30-day	xx.xx% (xx/xx)	[xx.xx%, xx.xx%]
1-year	xx.xx% (xx/xx)	[xx.xx%, xx.xx%]
2-year	xx.xx% (xx/xx)	[xx.xx%, xx.xx%]
3-year	xx.xx% (xx/xx)	[xx.xx%, xx.xx%]
All Cause MI		
30-day	xx.xx% (xx/xx)	[xx.xx%, xx.xx%]
1-year	xx.xx% (xx/xx)	[xx.xx%, xx.xx%]
2-year	xx.xx% (xx/xx)	[xx.xx%, xx.xx%]
3-year	xx.xx% (xx/xx)	[xx.xx%, xx.xx%]
Target Vessel MI		
30-day	xx.xx% (xx/xx)	[xx.xx%, xx.xx%]
1-year	xx.xx% (xx/xx)	[xx.xx%, xx.xx%]
2-year	xx.xx% (xx/xx)	[xx.xx%, xx.xx%]
3-year	xx.xx% (xx/xx)	[xx.xx%, xx.xx%]
Clinically-driven TLR		
30-day	xx.xx% (xx/xx)	[xx.xx%, xx.xx%]
1-year	xx.xx% (xx/xx)	[xx.xx%, xx.xx%]
2-year	xx.xx% (xx/xx)	[xx.xx%, xx.xx%]
3-year	xx.xx% (xx/xx)	[xx.xx%, xx.xx%]
Clinically-driven TVR		
30-day	xx.xx% (xx/xx)	[xx.xx%, xx.xx%]

1-year	xx.xx% (xx/xx)	[xx.xx%, xx.xx%]
2-year	xx.xx% (xx/xx)	[xx.xx%, xx.xx%]
3-year	xx.xx% (xx/xx)	[xx.xx%, xx.xx%]
Device Success ¹	xx.xx% (xx/xx)	[xx.xx%, xx.xx%]
Lesion Success ²	xx.xx% (xx/xx)	[xx.xx%, xx.xx%]
Procedure Success ³	xx.xx% (xx/xx)	[xx.xx%, xx.xx%]
Stent Thrombosis		
Discharge	xx.xx% (xx/xx)	[xx.xx%, xx.xx%]

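### SAP 4.4 opens the adverse-event window at stent implantation rather than at the start of the index procedure, and gives no clear start for enrolled subjects in whom no stent is implanted (minor)

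*SAP*

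**What the plan says.** SAP 4.4 (Adverse Events) defines a treatment-emergent adverse event (TEAE) as "an event that emerges, or a pre-existing event that worsens, any time during or after stent implantation". It continues: "The per-event and per-patient incidence of TEAEs will be presented overall and by MedDRA system organ class and preferred term". The same presentation is then repeated for serious TEAEs.

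Other parts of the documents use earlier time points:

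- **Recording from consent.** Protocol 7.2: "All adverse events (AEs) occurring following informed consent signature must be recorded".
- **First AE interval.** Protocol section 9, Detailed Explanations: "Adverse events occurring (1) from time of index procedure to 30 days follow-up contact".
- **Schedule.** In SAP 2.2.5, Table 1, the row "Record of adverse events" is marked from the Procedure column onward.
- **Start of procedure.** Protocol 7.2: "The start of the procedure is defined as the time of arterial cannulation".
- **Pre-dilatation.** Protocol 7.2: "the target lesion must be pre-treated with standard percutaneous transluminal balloon angioplasty". Direct stenting is not allowed.
- **AE definition.** Note 2 to Protocol 11.1.1 brings procedure-related events within the definition of an AE.
- **Objective.** SAP 2.1 says the long-term safety of the stenting procedure, complications included, will be "evaluated through clinical data obtained before, during and after stent placement".

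Enrolment, and so membership of the ITT set, occurs when the stent system enters the body (SAP 2.2.4, 4.2.1). Implantation is not required.

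**The concern.** Cannulation, angiography and pre-dilatation all come before implantation. An access-site bleed, a contrast reaction or a stroke in that interval would be recorded. Under the literal text of SAP 4.4 it would not enter AE or SAE incidence unless it later worsened. These are complications of the stenting procedure, which SAP 2.1 sets out to evaluate.

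The text and the table shells also point in different directions. Tables 12 and 13 have top rows for any AE and any SAE and state no window. One programmer could follow the text and another the row labels, and their counts could differ.

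Finally, the anchor is unclear where nothing is implanted. The shells allow for failed delivery (Table 6), a device that could not cross the lesion and was removed (Table 14), and a target lesion not treated with the study stent (Table 15). SAP 4.4 does not say whether a failed attempt, or a stent of another make, opens the window.

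The study is now descriptive only (SAP 4, 4.3.2), so its safety tables are among its main products.

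**Working it through.** **1. Order of events.** Protocol 7.2 gives the sequence consent, cannulation (start of procedure), baseline angiography, pre-dilatation, stent placement. The SAP 4.4 window opens only at the last of these.

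**2. Can another output recover the events?**

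| Output | Content | Shows a non-endpoint access, contrast or systemic event? |
|---|---|---|
| Tables 1.1, 1.2, 11a, 11b | Death, myocardial infarction (MI), revascularization, target vessel failure (TVF), stent thrombosis, acute success | No |
| Tables 6, 10, 14 | Procedural and angiographic findings, device problems | Only dissection, perforation, abrupt closure, device failure and similar |
| Tables 12, 13 | AEs and SAEs | Yes by row label; no under the literal text of 4.4 |
| Listings 1 to 3 | Demographics, history and acute success; lesions; device problems | No |

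SAP 4.3 promises individual data in subject listings, but none of the three listing shells is an AE listing.

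**3. Denominator.** The SAP gives no AE rate, so no AE figure can be reproduced. Its sample-size figure does reproduce: 65 × 0.93³ = 52.3, against about 52 stated in SAP 4.1. Those 52 are the subjects evaluable at 3 years. Tables 12 and 13 are headed by the ITT set, so the denominator here is the 65 enrolled subjects (SAP 2.2.2).

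**4. Size per affected subject.** A per-patient row changes only if the subject has no later event in that row. The change is then k/65 for k such subjects:

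- k = 0: 0 points (the case if onset is compared by date)
- k = 1: 1/65 = 1.5 points
- k = 2: 2/65 = 3.1 points
- k = 3: 3/65 = 4.6 points

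The range 0 to 3 is an assumption, because the documents give no rate of events before implantation.

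**5. A rare preferred term.** With exact (Clopper-Pearson) 95% limits, one subject in 65 is 1.5% (0.04% to 8.3%). If that subject is dropped, the row becomes 0/65, or 0% (0% to 5.5%), and the term leaves the table.

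**6. Subjects without an implant.** Entry to the ITT set requires only that the system enters the body, while the TEAE window requires implantation. Where the first occurs without the second, the text gives no definite start.

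**The case against.** Several arguments on the other side have force.

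- **The events at issue normally precede enrolment.** Access, angiography and pre-dilatation usually come before the study device enters the body. A window opening at implantation therefore lies close to the start of study treatment and of ITT membership. A subject with a serious access complication may never receive the device and so never be enrolled. Counting pre-device events only in those later enrolled is not a fully unbiased incidence either. This stands, and the fix has to say so.
- **Collecting more widely than one analyses is not itself a conflict.** Worsening of a pre-existing event cannot be judged without earlier recording. A reader might infer that recording from consent contradicts the TEAE window; the documents do not support that. The case rests on the procedure-inclusive AE definition, the SAP 2.1 objective and the unrestricted table shells.
- **The loss may be nil.** The SAP's follow-up windows are in days and its compliance table counts from the procedure date. Neither document says that AE onset is compared by clock time. If onset is compared by date, events on the day of the procedure are counted. This stands.
- **Implantation can be read loosely.** It may mean the whole stenting procedure. The protocol appendix times thrombosis from implantation yet sets time zero after the subject leaves the laboratory, so the term is not used as one exact moment. On that reading a failed delivery may also be covered. But SAP 4.4 does not say this, and Protocol 7.2 defines the procedure start separately.
- **If the table labels govern, nothing is omitted.** True, but text and labels then still disagree.

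None of this returns the excluded events to the incidence tables under the literal wording. It does reduce the point to a clarification.

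**Conclusion.** The point holds as a minor one. SAP 4.4 opens the AE window later than the start of the index procedure and leaves it without a clear start for ITT subjects with no stent implanted. Taken literally, it omits from AE and SAE incidence the non-endpoint events of access, angiography and pre-dilatation that do not later worsen.

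The effect is between zero and 1.5 points per affected subject. It is zero if onset is compared by date. If onset time is used, an assumed 0 to 3 subjects gives 0 to 4.6 points on a row, with 65 as denominator.

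Two stronger readings are tempting. One is that the reported AE rates will be understated. The documents establish neither that clock times are used nor that such events will occur, so an actual understatement is not shown. The other is that the study's safety conclusions are compromised. TVF, death, MI, revascularization and stent thrombosis are tabulated separately, as are the complications in Tables 6, 10 and 14, and none of these depends on the TEAE window.

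**What to change.** In SAP 4.4, define a TEAE as an event with onset or worsening at or after the start of the index procedure, in any enrolled subject, whether or not a stent is implanted. Take the start as arterial cannulation, or as the procedure date if no onset time is available.

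In footnotes to Tables 12 and 13, state this window and the denominator (all enrolled subjects). A denominator note is useful in any case, because SAP 4.3 describes the event rate by reference to the subjects with adverse events. Add that anyone who had an event before the device was introduced and was never enrolled is not in the denominator.

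The cost is one sentence and two footnotes. No new data are needed, since AEs are already recorded from consent. The downside is that counts may rise slightly and will include events due to access or angiography rather than to the stent.
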